- Brief interventions (BIs) are potentially effective and low-cost treatments for hazardous alcohol use. BIs typically consist of a 5-15 minute single counseling session (with possible booster sessions) administered by a primary care physician or nurse and include components such as: feedback on use and the harm drinking may be causing, norm referencing, identifying coping strategies, and motivational enhancement for changing behavior. Literature from high income countries suggests that BIs delivered in primary care settings can be both cost and clinically effective in reducing alcohol consumption for hazardous/harmful drinkers and mild AUD, including among PLWH. Evidence for the effectiveness of single-session BIs in SSA among PLWH is limited; two studies conducted in Uganda and South Africa found that alcohol consumption decreased among PLWH who received a BI but not significantly greater than a control condition.
- In addition to BIs, multi-session psychological treatments, such as cognitive behavioral therapy (CBT)-based approaches, are needed to address more severe AUD. BIs were designed to address hazardous use and other sub-threshold alcohol problems but are not intended as a stand-alone treatment for moderate-to-severe AUD or comorbidities (defined in this study as mental health or non-alcohol substance use issues). Conversely, CBT is an evidence-based psychological treatment for AUD and mental health disorders. A review of AUD interventions among PLWH found that CBT was particularly promising.

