### Stage 1B:

Study participants will be PLWH who are currently receiving care at one of the two study clinics. Participants will be recruited by their regular care providers (i.e., peer educators, counselors, nurses, physicians) and referred to study staff if they are interested. We anticipate enrolling a total of 320 participants, all of whom have hazardous alcohol use. 50% of them will be lower-risk drinkers who do not have moderate-to-severe alcohol use disorders (AUD) or mental health comorbidity. These participants will be part of the 'Cohort Study'. These will not be randomized. The other 50% will be high-risk drinks due to having either moderate-to-severe AUD or mental health comorbidities, or both. This second group will be randomized into the RCT Study. The minimum age of research subjects will be 18. All subjects will be recruited from our two study clinics. Eligibility will be assessed via audio computer assisted self-interviewing (ACASI).

*Initial* inclusion criteria for overall enrollment (into either the Cohort or RCT study) will be:

- HIV positive
- Receiving HIV treatment services at one of the two study clinics
- Current hazardous alcohol use, defined as an AUDIT score of  $\geq 8$  for men and  $\geq 4$  for women
- Provides informed consent

*Secondary* inclusion for enrollment into the RCT will be:

- AUDIT scores that indicate a moderate-to-severe AUD ( $\geq 12$  for women;  $\geq 16$  among men)
- AND/OR: meeting validated symptom criteria for depression ( $\geq 16$  on CES-D), trauma/anxiety ( $\geq 2.5$  on HTQ), and/or substance use ( $\geq 27$  for any non-tobacco/alcohol substance on ASSIST)

Participants who meet initial inclusion criteria AND secondary inclusion criteria will be eligible for the RCT. Participants who meet initial inclusion criteria but NOT secondary inclusion criteria will be eligible for the Cohort study.

- **Exclusion Criteria:**

Stage 1A: No formal exclusion criteria.

Stage 1B: Study exclusion criteria for Stage 1B (applies to the Cohort study and the RCT) will be:

- HIV negative

- Not receiving care at one of the study clinics
- Currently psychotic or on an unstable psychiatric drug regimen
- Actively suicidal: Suicide attempt or suicidal ideation with intent or plan, or self-harm in the past month.
- Unable to provide informed consent

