1. Screening for eligibility into the overall study. Participants will provide informed consent for the screening activity. They will then complete a screener that consists of demographic information and the Alcohol Use Disorders Identification Test administered via the audio computer assisted self-interviewing (ACASI). Eligibility criteria for this stage are:

- HIV positive
- Receiving HIV treatment services at one of the two study clinics
- Current hazardous alcohol use, defined as an AUDIT score of  $\geq 8$  for men and  $\geq 4$  for women

Following the ACASI screener, the ACASI system will alert the assessor if the participant is eligible or not. If not eligible, the participant will exit the study. If eligible, the participant will conduct the secondary screening to determine whether they will be part of the cohort or the RCT. The additional screening questions will also be administered via ACASI. Participants will be enrolled into the cohort study unless one or more of the following conditions are met:

- AUDIT scores that indicate a moderate-to-severe AUD ( $\geq 12$  for women;  $\geq 16$  among men)
- AND/OR: meeting validated symptom criteria for depression ( $\geq 16$  on CES-D), trauma/anxiety ( $\geq 2.5$  on HTQ), and/or substance use ( $\geq 27$  for any non-tobacco/alcohol substance on ASSIST)

If any of these conditions are met, the participant will be eligible for and enrolled into the RCT.

Cohort study participants (i.e., lower risk participants) will not be randomized. They will receive the brief alcohol intervention and we will conduct a 6 month post-baseline assessment. The purpose of including them in the study is to gain some preliminary data on whether the brief intervention may be helpful in reducing alcohol consumption among these participants that have a lower level alcohol use problem and no significant mental health or other substance use comorbidities. They are not formally included in the RCT because we did not have the resources to do so in this pilot grant.

RCT participants (i.e., higher risk participants) will be randomized to receive either the brief intervention alone or the brief intervention + CETA. Similar to the cohort participants, we will conduct a 6 month post-baseline assessment among all RCT participants. The purpose of the RCT is to assess whether the BI

alone is effective or whether a more substantial intervention (BI +CETA) is necessary for these higher risk participants.

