Baseline data collection. The baseline assessment will be conducted via ACASI. The participant will first complete the Alcohol Use Disorders Identification Test (AUDIT) to assess eligibility into the study. The ACASI will automatically alert the assessor if the participant is eligible based on the hazardous alcohol use criteria. If eligible, the participant will complete the remaining measures: (1) Center for Epidemiological Studies-Depression Scale (CES-D); (2) Harvard Trauma Questionnaire (HTQ); and (3) the Alcohol, Smoking, and Substance Involvement Screening Test (ASSIST). All of these measures have previously been translated and used by our team in Zambia and the AUDIT, CES-D, and ASSIST measures have been formally validated. A research assistant will be available if there are any challenges with the ACASI. Additionally, we will use HIV clinic files to extract HIV-related data. These data are captured as part of HIV routine care in Zambia and include: (1) ART initiation date, (2) hepatitis B surface antigen, (3) most recent CD4+ count, (4) cumulative and past 6-month ART retention, defined by medication possession ratio (MPR; an objective pharmacy record metric that we have used previously) and (5) plasma HIV viral load (measured at CIDRZ Central laboratory using the Roche COBAS/Ampliprep platform).

Secondary eligibility criteria for the RCT. Following completion of the baseline assessment, ACASI will automatically alert the assessor if the participant is eligible for the pilot RCT via a built-in algorithm. Criteria for the RCT will be (a) AUDIT scores that indicate a moderate-to-severe AUD ( $\geq 12$  for women;  $\geq 16$  among men) and/or (b) meeting validated symptom criteria for depression ( $\geq 16$  on CES-D), trauma/anxiety ( $\geq 2.5$  on HTQ), and/or substance use ( $\geq 27$  for any non-tobacco substance on ASSIST).

Randomization. Participants eligible for the pilot RCT will be randomized 1:1, stratified by sex, to receive the BI alone or BI+CETA. Participants who are NOT eligible for the pilot RCT will be provided with a BI but will not be randomized.

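### The ASSIST route into the RCT is stated two ways: one statement of the rule omits the exclusion of alcohol, so a lower-risk drinker could be randomised instead of entering the cohort

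*Combined protocol and SAP*

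**What the plan says.** The rule for sending a Stage 1B participant to the RCT or the cohort appears three times. The AUDIT, CES-D and HTQ cut-offs and the ASSIST cut-off of 27 are the same each time. The substances that count on ASSIST are not.

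- **Section IV, Participants, Stage 1B (secondary inclusion):** 27 or more "for any non-tobacco/alcohol substance on ASSIST".
- **Section V, Consent Process, eligibility screening:** the same wording, excluding tobacco and alcohol. This text adds: "The additional screening questions will also be administered via ACASI".
- **Section V, Study Implementation, Stage 1B (secondary eligibility criteria for the RCT):** 27 or more "for any non-tobacco substance on ASSIST". The same paragraph says: "ACASI will automatically alert the assessor if the participant is eligible for the pilot RCT via a built-in algorithm".

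Three other statements bear on the intended meaning. Section II gives the study's definition: "comorbidities (defined in this study as mental health or non-alcohol substance use issues". The screening text describes cohort members as having a "lower level alcohol use problem and no significant mental health or other substance use comorbidities". The Stage 1B paragraph lists "AUDIT scores that indicate a moderate-to-severe AUD" as criterion (a), apart from the symptom and substance criteria in (b).

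**The concern.** ASSIST covers alcohol; its full name in the protocol is "the Alcohol, Smoking, and Substance Involvement Screening Test (ASSIST". A rule that removes only tobacco therefore leaves alcohol among the qualifying substances. Everyone screened at this point is already a hazardous drinker, and alcohol severity already has a route into the RCT through AUDIT (12 or more for women, 16 or more for men). Read literally, the Stage 1B paragraph adds a second alcohol route that bypasses those cut-offs.

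The classification decides which second consent form the person is given, whether they are randomised, and whether CETA can be offered. It also defines the cohort, which is meant to estimate the within-group effect of the brief intervention in lower-risk drinkers. An operative entry rule should have one meaning, and a randomisation made under the wrong one cannot be undone.

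**Working it through.** **1. The plan's own sizes (section III.B).** Inputs: standardised difference 0.5, alpha 0.05 (two-sided assumed, since the plan does not say), power 80%, 1:1 allocation, 20% dropout, 50% of hazardous drinkers qualifying for the RCT.

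- Per arm, two-sample t-test: 63.77, rounded up to 64; total 2 × 64 = 128. The normal approximation gives 63 per arm.
- Dropout: 128 / (1 − 0.20) = 160.
- Hazardous drinkers to enrol: 160 / 0.50 = 320.

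All three match the plan. Harmonising the ASSIST wording changes none of them.

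**2. One person under each statement of the rule.** Take a man with AUDIT 8–15 or a woman with AUDIT 4–11, CES-D below 16, HTQ below 2.5, no other drug at 27 or more on ASSIST, and an ASSIST alcohol score of 27 or more.

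| Step | Section IV and screening text | Stage 1B paragraph |
|---|---|---|
| Initial entry (AUDIT ≥8 men, ≥4 women) | met | met |
| AUDIT route (≥16 men, ≥12 women) | not met | not met |
| Depression or trauma route | not met | not met |
| ASSIST route | not met (alcohol excluded) | met (only tobacco excluded) |
| Assigned to | cohort | RCT |

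The definition in section II and the description of the cohort both agree with the middle column.

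**3. How large it could be.** Let f be the share of intended cohort members who fit step 2. The documents give no value for f, so the values below are assumptions for illustration.

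- RCT-eligible share of hazardous drinkers: q = 0.50 + 0.50 × f.
- Intended cohort members among 160 randomised: 160 × (0.50 × f) / q.

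| Assumed f | q | Misplaced among 160 randomised |
|---|---|---|
| 0% | 50% | 0 |
| 1% | 50.5% | 1.6 |
| 5% | 52.5% | 7.6 |
| 10% | 55% | 14.5 |
| 20% | 60% | 26.7 |

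For example, at f = 10%: 160 × 0.05 / 0.55 = 14.5. If instead enrolment were held at 320 with no cap on the RCT, the number moved would be 160 × f, or 16 at f = 10%.

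**The case against.** The strongest reply is that this is a drafting slip whose intended meaning is plain. Section IV, the screening text, the section II definition and the cohort description all point the same way, and the Stage 1B paragraph itself keeps alcohol under AUDIT. That is persuasive about intent, and the divergent phrase is probably an omission. It does not remove the need to correct it, because the phrase sits in an operative eligibility paragraph.

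A reader might infer that the Stage 1B wording is the one ACASI applies, since only that paragraph mentions a built-in algorithm. The documents do not support this. Section IV also says eligibility is assessed by ACASI, and the screening text gives the secondary questions by ACASI. Nothing shows which statement the code follows.

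A reader might also infer that the two clinics, or two software builds, would classify the same person differently. The protocol describes a single algorithm and gives no sign of separate builds.

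Nor do the documents show that the cohort would lose its heaviest drinkers. The AUDIT cut-offs already move the more severe drinkers to the RCT by design, and nothing relates an ASSIST alcohol score of 27 to consumption among those who remain.

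**Conclusion.** The inconsistency is certain: it can be read directly from current text. Its consequence is conditional. Misplacement needs code that follows the Stage 1B paragraph literally and participants with ASSIST alcohol at 27 or more, AUDIT below the RCT cut-off and no other qualifying condition. The documents give no data on that overlap, and the group may be empty. So the supportable statement is that some lower-risk drinkers could be randomised, not that they would be.

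The stronger conclusion that the trial comparison would be biased does not follow. Eligibility is settled before the envelope is opened, so any extra entrants would be allocated 1:1 like everyone else. The possible damage is to the make-up of the two groups: the RCT could include people the plan assigns to the cohort, and the cohort's before-after estimate would be drawn from a narrower group than described. This is worth correcting because it concerns an entry rule and correction is nearly free, not because a large effect has been shown.

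**What to change.** In the Stage 1B paragraph on secondary eligibility, replace the ASSIST phrase with the wording already used in section IV and the screening text, "for any non-tobacco/alcohol substance on ASSIST". All three statements then agree with each other and with the definition in section II.

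Before enrolment, check the coded ACASI rule against that wording. A test record built as in step 2 of the working is enough: it should return cohort.

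The cost is one phrase in the protocol and a short code check. No sample size or analysis changes.

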### Interventions

- World Health Organization mhGAP BI. All participants (regardless of whether RCT criteria are met) will receive a BI. We will provide training to lay counselors (e.g., counselors/nurses already working in the HIV clinics) based on World Health Organization (WHO) mhGAP-Intervention Guide (mhGAP-IG). The mhGAP-IG was developed to provide non-specialists in LMIC with knowledge and skills to deliver low-intensity interventions with fidelity in primary care to treat mental, neurological, and substance use problems. WHO has developed modules to train health care workers. The JHU clinical team in Zambia will adapt these modules to provide a 2-day workshop for counselors at our two clinics. Training will cover components such as: (1) psychoeducation (e.g., examples of ways that hazardous use can be reduced); (2) engagement (e.g., discussing motivations for drinking); (3) personalized feedback and advice (e.g., helping the participant reflect on how use is impacting their life); and (4) encouragement for the participant to change their pattern of use.

Following the baseline assessment, the assessor will notify the on-duty counselor who has been trained in the BI. The BI, which is expected to take 10-15 minutes, will be offered to participants the same day and provided in a private room.

- [Common Elements Treatment Approach \(CETA\)](#). Lay counselors (e.g., HIV peer educators, counselors in the HIV clinics) will be trained to deliver CETA to participants randomized to BI+CETA (i.e., n=80). After enrollment, participants receiving CETA will flexibly meet with their counselor weekly for approximately one-hour sessions, for 6-12 weeks depending on presentation and symptom level. Core elements of CETA sessions are described in Table 2 and will be adapted as needed in Stage 1A.

**Table 2.** Common Elements Treatment Approach

Component	Content	Target
Engagement	Discuss how program helps Identify obstacles to engagement	Promote client buy-in
Safety	Assess client risk for harm to self/others Domestic violence/abuse assessment Initiate safety plan as needed	Assess and address client safety
Empirically-supported cognitive-behavioral elements		
Psychoeducation/Introduction	Program information, normalize symptoms, goal setting	Psychoeducation Reduce stigma
CBT for alcohol and other substance use	CBT and MI integrated element to set goals and reduce use; Identification and strategies for addressing drivers of use	Reduce alcohol/substance use Increase social support
Behavioral Activation	Identify and engage in pleasurable activities	Reduce depressive symptoms; Facilitate engagement in helpful programs
Cognitive Coping/Restructuring	Identify and correct thoughts, feelings, and behaviors Replace unhelpful thoughts with helpful ones	Reduce depressive, anxious, and trauma-related symptoms; Reduce self-blame and stigma; Reduce negative thoughts on HIV care
Relaxation	Breathing exercises, imagery	Reduce anxiety and stress-related symptoms
Exposure	Talk about trauma memories or confront fears using gradual desensitization	Reduce trauma and anxiety symptoms
Problem Solving	Teach a process of steps to solve problems and make healthy decisions	Promote health decision making Skills training for problem solving

CETA will be delivered within the clinic with an option for community-based delivery (i.e., in a local church or community center) if preferred by the participant, similar to previous Zambia studies. To estimate uptake of CETA in a “real-world” HIV clinic setting, if participants do not attend their initial meeting, counselors will make several phone follow-ups for up to a maximum of 1 month after enrollment. If the participant does not start treatment within one-month post-enrollment, the counselor will cease efforts to engage them in CETA as additional retention efforts would be impractical in a non-research setting. After the initial session, if a client misses a follow-up appointment, the counselor will again follow-up by phone up to three times in a week and make a one-time home visit to re-engage the client. The research team will not contact the participant during the active intervention phase so as not to artificially influence the participant to attend CETA sessions.

[Tracking of treatment uptake and completion.](#) We have developed rigorous and sophisticated participant tracking systems through our previous Zambia studies. We will systematically track throughout the course of the study: (1) the number of participants who successfully complete and decline BI; (2) the number of participants who successfully link to CETA, defined as attending the first CETA session; (3) the amount of time counselors dedicate to client tracking/retention; and (4) the number of clients who successfully complete CETA. Counselors will attempt to track clients to the extent that this would be practical in a real-world setting.

[Clinical monitoring data collection.](#) During CETA sessions, the counselor will administer a brief clinical symptom checklist (Client Monitoring Form; CMF) and a past 7-day Alcohol TLFB. These data guide clinical care by informing the choice of CETA elements to be delivered in session and will also be used in analyses. These forms will only be administered to CETA participants during their CETA sessions. (Neither RCT participants randomized to the BI alone nor Cohort study participants will complete the TLFB).

Follow-up assessments. Alcohol and comorbidities will be assessed in all participants at 6 months (i.e., endline) after baseline. The ACASI questionnaire that was used at baseline will again be administered at this follow-up visit (i.e., the questionnaire at this visit is the same as at baseline). In addition to ACASI assessments, we will confirm self-reports of alcohol abstinence on the AUDIT by conducting a urine-based rapid alcohol biomarker test, ethyl glucuronide (uEtG). Finally, at the 6-month post-assessment, which coincides with a regularly scheduled clinic visit, we will extract relevant information from the client's HIV clinical record (this will be the same information that is collected at baseline), including: , (1) hepatitis B surface antigen, (2) most recent CD4+ count, (4) cumulative and past 6-month ART retention, defined by medication possession ratio (MPR; an objective pharmacy record metric that we have used previously) and (4) plasma HIV viral load (measured at CIDRZ Central laboratory using the Roche COBAS/Ampliprep platform). We will not collect any additional biospecimens for purposes of the study—all HIV-related data will be captured via chart extraction. To supplement retention data captured through MPR measurement, we will also assess visit adherence, the percentage of assigned pharmacy and clinical visits that were made (coming to clinic within 3 days).

Implementation data collection. We will conduct a mixed methods process evaluation with stakeholders involved in the CETA referral and treatment process, including follow-up FGDs and KIIs with participants from Stage 1A and CETA counselors. We will also conduct mixed methods interviews with approximately N=30 PLWH who participated in the Stage 1B pilot RCT. This will include a purposeful sample of PLWH from a range of ages and both sexes who did and did not complete the BI and CETA. Implementation factors to be explored will include: acceptability, appropriateness, reach, cost, feasibility, and sustainability and will explore the attitudes, thoughts, feelings, and barriers and facilitators related to implementation. Interviews will include an in-depth interview component and JHU quantitative implementation measures.

Data management. All uptake/completion, clinical monitoring, HIV outcome, and uEtG data will be double entered into password protected databases by research staff weekly. ACASI data will be electronically transferred from field laptops at the HIV clinics into the study database at CIDRZ headquarters daily. De-identified data will be transferred to JHU weekly. [name] will run data checks and return queries for resolution. [name] and [name] will hold weekly calls with the Zambian data team.

- Describe the number and type of study visits and/or contacts between the study team and the participant, how long they will last, and where/how they will take place.

Stage 1A: We expect to have two study visits with focus group participants (PLWH and healthcare workers). The first visit will be the recruitment/consent visit. The second visit will be the actual focus group session. The first visit we expect to take approximately 30 minutes. We expect the focus groups to be between 60-90 minutes. We expect to have one study visit for key informants in which we will conduct both the consent and interview. We expect these sessions to be approximately 60-90 minutes. A third contact may be conducted with some of the healthcare workers and key informants at the end of the study to discuss implementation factors in an in-depth interview or focus group. This third visit will be approximately 60-90 minutes in length.

Stage 1B: Participants in the pilot will have an initial study visit for consent/screening/baseline/BI. The initial visit, which includes informed consent and baseline ACASI to capture data, may take up to 120 minutes. If they are randomized to CETA they will have an additional 6-12 weekly therapy sessions (approximately 60 minutes each). All participants will have a post-assessment visit approximately again 6 months post-baseline (we will attempt to have the 6 month assessment align with a regular HIV care visit). The follow-up study assessments we expect to take approximately 45 minutes. We will also ask a sample of participants to participate in a mixed methods interview following the study on implementation outcomes.

- Describe the expected duration of the study from the perspective of the individual participant and duration overall.

From the perspective of participants, the study will be approximately 6 months. Overall, we expect the study to take 3 years, including final data analysis. An estimated timeline is provided below.

**Table 4.** Study timeline

Study Phase	Activity	Year 1				Year 2				Year 3			
		Q 1	Q 2	Q 3	Q 4	Q 1	Q 2	Q 3	Q 4	Q 1	Q 2	Q 3	Q 4
Planning	Study protocol finalization and ethical approval												
	Staff hiring and site preparation												
	Training of qualitative data staff												
Stage 1A	Focus groups and key informant interviews												
	Adaptation of CETA for PLWH												
	Development of CETA protocol in HIV care based on Stage 1A												
	CETA/mhGAP-IG trainings, assessor trainings, M&E trainings												
Stage 1B	CETA pilot cases												
	Recruitment, consent, screening and baseline assessments (ACASI, HIV)												
	Interventions active												
	Post-treatment assessments (ACASI, UEtG)												
	6-month outcomes assessment (ACASI, UEtG, HIV outcomes via chart review)												
Analysis, dissemination, and next steps	Implementation data collection (PLWH, clinic staff, policy officials)												
	Data analysis												
	Report/manuscript writing and dissemination at conferences												
	Preparation and submission of follow-up R01												

- Provide a brief data analysis plan and a description of variables to be derived.

*Analysis of treatment uptake and completion.* We will estimate a logit model with a binary outcome (1=completer; 0=non-completer) to assess predictors of treatment completion. Predictors will be demographic (e.g., sex, age), clinical (e.g., symptom severity), and structural (e.g., distance from clinic) level factors.

*Analysis of ACASI outcome data.* Analyses will be intent-to-treat. AUDIT score, along with other continuous secondary outcomes (Past 30-Day TLFB [% days drinking and mean drinks per day], CES-D, HTQ, ASSIST scores) will be modelled with linear mixed models. Fixed effects will include treatment arm (0=BI; 1=BI+CETA), time (0=Baseline; 1=6-months post-baseline), and interaction terms between treatment arm

and time. This will allow estimation of the mean difference in change in score between arms and 95% confidence intervals. Cohen's D will be calculated to estimate effect size. Covariates will be included if they differ meaningfully at baseline or predict significant change in the outcome. For dichotomous outcomes or non-normally distributed continuous outcomes, generalized linear mixed effects models will be estimated. Paired t-tests will be used to assess within group change among the non-Pilot RCT hazardous drinkers.

*Analysis of CETA clinical monitoring data.* We will conduct longitudinal data analysis with CMF and TLFB daily estimates of drinking during CETA. Exploratory analysis will examine trajectories of weekly symptom change based on CMF score and number of drinks per day using spaghetti and scatter plots. We will explore the association between baseline client characteristics on symptom trajectories. We will use survival analysis to calculate the number of sessions required for 25%, 50%, and 75% of clients to achieve one or two standard deviation(s) in symptom improvement from baseline. We will also calculate the percentage of clients that achieve these changes by the end of treatment. Collectively, these analyses will provide insight into *when* symptoms change over the course of treatment, which may be useful in refining CETA in future studies.

*Analysis of HIV outcome data.* In both RCT and non-RCT participants, we will use a linear model to investigate changes to MPR during the period before and after the intervention and a logistic model for changes to the proportion with HIV viral suppression (defined as <1000 copies/ml, the standard in SSA). We will compare visit adherence between those randomized to BI+CETA versus BI alone. Because of the relatively small sample sizes in this pilot study, these data will be primarily descriptive; however, these data will inform a follow-up grant.

*Analysis of uEtG results.* The purpose of uEtG testing is to confirm abstinence and not to validate AUDIT scores >0. Based on Preliminary Studies we expect to identify 'under-reporters,' defined as participants who report abstinence on AUDIT or TLFB and test uEtG-positive. In a secondary analysis, we will exclude under-reporters and re-assess the impact of the intervention on alcohol use and other outcomes.

*Analysis of implementation data.* Mixed methods analysis based on NIH best practice guidelines will be used to integrate findings from the quantitative and qualitative data. Descriptive analyses will be used to investigate the quantitative data on constructs of acceptability, appropriateness, reach, feasibility, and cost. The qualitative data will provide in depth understanding of factors related to (1) mechanisms of change; and (2) barriers and facilitators to program implementation in the Zambian context. Findings will be shared with local (HIV clinics, Lusaka district, and Zambia MoH) and international stakeholders (PEPFAR/CDC, UNAIDS, etc.) to inform future programming efforts.

5. **Answer the following if they are relevant to your study design:**

1. If the study has different arms, explain the process for assigning participants (intervention/control, case/control), including the sequence and timing of the assignment.

The assessor will have two locked cabinets at the clinic with sealed envelopes. One cabinet will contain randomization assignments for female participants, the other for male participants. Printed on the outside of the sealed envelopes will be a Randomization ID. When a participant is eligible for the pilot RCT, the assessor will retrieve the next available envelope and record the Randomization ID and Screening ID on a Screening Information Sheet, thus linking the two IDs to the participant. Randomization IDs will be assigned to BI+CETA or BI alone using *randomize* in Stata *a priori* by a U.S.-based statistician not affiliated with the study. Randomization IDs will be randomized 1:1 in blocks of 20 stratified by sex. The assessor will inform the participant of their assignment by opening the envelope

immediately after the baseline assessment. This ensures that the assessor is blinded to the participant's randomization status during the assessment itself. Follow-up assessments will be conducted by a different assessor.

2. If human biospecimens (blood, urine, saliva, etc.) will be collected, provide details about who will collect the specimen, the volume (ml) and frequency of collection, how the specimen will be used, stored, identified, and disposed of when the study is over. If specimens will be collected for use in future research (beyond this study), complete the "Biospecimen Repository" section below.

The only biospecimen being collected in this study will be a urine ethyl glucuronide (ETG) test to confirm alcohol abstinence. In previous alcohol research conducted by our team in Zambia, we have found that it is important to compare self-reported alcohol use to an objective biomarker. This urine specimen will only be collected at one timepoint among cohort and RCT participants: at the 6-month post-baseline assessment. The test requires the participant to provide a small urine sample (appx. 100ml). During the study visit we will provide participants with a urine cup and ask them, in a private bathroom at the clinic, to provide us with a 100ml sample of urine. Following the sample collection, a study assessor will insert a dipstick into the sample and within 1 minute the test provides a qualitative (positive/negative) result for alcohol consumption within the past 2-5 days.

We will provide participants with results of the EtG test at the visit. No additional tests except the dipstick will be conducted with the sample. Following testing, the sample will be destroyed. We have used EtG tests previously with similar patient populations and it was found to be feasible and acceptable ([name] et al., 2018).

3. If genetic/genomic analyses are planned, address whether the data will be contributed to a GWAS or other large dataset. Address returning unanticipated incidental genetic findings to study participants.

N/A

4. If clinical or laboratory work will be performed at JHU/JHH, provide the JH Biosafety Registration Number.

N/A

5. If you will perform investigational or standard diagnostic laboratory tests using human samples or data, clarify whether the tests are validated and/or the lab is certified (for example is CLIA certified in the U.S.). Explain the failure rate and under what circumstances you will repeat a test. For all human testing (biomedical, psychological, educational, etc.), clarify your plans for reporting test results to participants and/or to their families or clinicians. Address returning unanticipated incidental findings to study participants.

The urine dipstick ETG test has been FDA-approved and validated.

Urine dipstick results (positive or negative) for ETG will be discussed with participants as soon as they are available (within 1 minute of sample collection).

6. If your study involves medical, pharmaceutical or other therapeutic intervention, provide the following information:

1. Will the study staff be blind to participant intervention status?

Assessors will be blind to participant intervention status. Due to the nature of the interventions, counselors will not be blinded. Data Analysts will also be blinded.

2. Will participants receive standard care or have current therapy stopped?

Participants are already receiving standard of HIV care in Zambia and this will be continued during and after the study. Participants will not be asked to stop any current therapy.

3. Will you use a placebo or non-treatment group, and is that justifiable?

We will not have a non-treatment group. The control group will receive the BI, which is the current standard of care at HIV clinics in Zambia.

4. Explain when you may remove a participant from the study.

Participants will be temporarily removed from the study if they demonstrate actively suicidal or homicidal thoughts. Anyone who develops psychosis in need of hospitalization will also be removed. In any of these events, research assistants, counselors, and supervisors will work together to get appropriate psychiatric assistance for the individual. The study PI and our clinical supervisory team will consult with psychiatric providers in Zambia to determine whether the participants may return to the study following appropriate treatment.

Participants will be removed from the study at their request if they express to us that they do not feel safe.

5. What happens to participants on study intervention when the study ends?

Study interventions will be completed before the end of the study. Following the end of the study, participants who request additional services will be referred to appropriate care.

6. Describe the process for referring participants to care outside the study, if needed.

Some participants may experience emotional distress as a result of participation. Many therapeutic interventions deal with small degrees of stress within a session as part of the treatment. Based on research and experience, the expected degree of distress will be minimal and expected as part of the therapeutic process. In cases where distress does occur during treatment, the participant would be with a trained counselor who will be trained at handling such situations. In addition, these

counselors will have local supervisors; and access to [name] (co-I; Licensed Clinical Social Worker) and [name] (co-I; Clinical Psychologist) and [name] (consultant; psychiatrist, University of Zambia). Our team has run multiple trials with CETA, including in Zambia, and have not found this to be a problem. We are prepared to handle more significant issues that could arise and have established relationships at Chainama Hills Hospital in Lusaka, which has inpatient psychiatric services. Should it be necessary, participants can be referred and receive treatment there.

